## SYNOPSIS

Title	Proactive against reactive therapy for the prevention of lichen sclerosis exacerbation and progression of disease – a pragmatic, parallel group randomised controlled trial with embedded economic evaluation and process evaluation
Acronym	PEARLS
Short title	ProactivE Against Reactive treatment for Lichen Sclerosus
Chief Investigator	[name]
Objectives	
Aim: To compare the clinical and cost effectiveness of a twice weekly topical corticosteroid maintenance strategy (proactive therapy) with as required treatment (reactive therapy) in the management of vulval lichen sclerosis (LS).
 
Primary Objectives: Compare the effectiveness of proactive versus reactive strategies for using topical corticosteroids on the number of flares within 12 months, in people aged <math>\geq 5</math> years with vulval lichen sclerosis (LS).
 
Secondary objectives:
 
 
1. Assess the effectiveness of proactive versus reactive use of topical corticosteroids (TCSs) over 24 months in reducing disease progression.
 
2. Assess the clinical effectiveness of proactive versus reactive strategies for the management of vulval LS for up to 24 months.
 
3. Assess the safety of using potent and superpotent TCSs in the vulval area over 24 months.
 
4. Assess the cost-effectiveness of the two treatment strategies.
 
5. Understand the acceptability of reactive and proactive long-term treatment strategies and the barriers and facilitators to continuing with prescribed treatment.
 

Trial Configuration	2-arm, parallel-group, randomised, open label assessor-blinded, multicentre, superiority trial with an internal pilot phase.

Internal pilot	The internal pilot phase will test the recruitment of sites and participants against agreed milestones. A formal review will take place 6 months after the first randomisation.
Setting	Primary care centres may act as participant identification centres (PICs), recruitment is via secondary care hospitals throughout the UK or specialist community hubs
Sample size estimate	Based on the likelihood ratio test statistic for comparison of two negative binomial rates, 320 participants for analysis are required to detect a relative reduction of 25% in number of flares, from an average of 4 flares per participant per year in the reactive therapy to 3 in the proactive therapy (absolute reduction of 1 flare per patient in a year), with 90% power, 1:1 allocation and a two-sided significance level of 0.05, using dispersion parameter value of 0.34 estimated from our survey data. To allow for ~20% non-collection of primary outcome data and treatment non-compliance, we plan to recruit 400 participants in total.
Number of participants	400
Eligibility criteria	
INCLUSION CRITERIA
 
 
1. Clinical or biopsy confirmed diagnosis of vulval LS
 
2. Currently controlled disease (asymptomatic with minimal clinical evidence of active disease) at baseline
 
3. Age <math>\geq 5</math> years
 
4. Able to give consent/child assent plus parental consent
 
 
EXCLUSION CRITERIA
 
 
1. Previous vulval intraepithelial neoplasia (VIN) or vulval squamous cell carcinoma (SCC)
 
2. Contraindications to topical steroids
 
3. Concomitant use of other topical anti-inflammatory vulval treatments
 
4. Using systemic immunosuppressants (for any indication)
 
5. Using systemic treatment for LS
 
6. Patients with surgical alteration of vulval skin as part of gender reaffirming surgery, or patients not born with a vulva
 
7. Pregnant and breastfeeding women
 

Description of interventions	Intervention: Potent or superpotent TCS, used for two non-consecutive days per week, even in absence of symptoms ('proactive treatment')

	
Control: Treat flare as required with potent or superpotent TCS ('reactive treatment') daily until flare resolves (typically up to 7 days)

Duration of trial	Expected duration of the trial is 57 months from the start of set-up
Randomisation and blinding	
Eligible patients who consent will be individually allocated in a 1:1 ratio to either proactive or reactive use of TCS. Treatment will be assigned randomly using a minimisation algorithm with a random element, balancing across groups on:
 
 
• recruitment site
 
• age at randomisation 
 
- children – 5 to <12 years
 
- adolescent – 12 to <16 years
 
- adult – 16 to <45 years
 
- perimenopausal - 45 years & above
 
 
 
• time since last flare (<math>\leq 6</math> months, <math>> 6</math> months)
 
• strength of TCS prescribed (potent or superpotent)
 
 
Allocation will be concealed using a web-based algorithm and held on a secure server, accessed via a secure website.
 
It is not possible to blind the participants, but independent examining clinicians will make assessments of disease activity and scarring at 12 and 24 months and will be blinded to treatment allocation.

Outcome measures	
PRIMARY OUTCOME: Number of flares over 12 months. Flare is defined as worsening of symptoms requiring increased application of TCSs.
 
SECONDARY OUTCOMES: Clinical effectiveness
 
 
• Progression of scarring assessed by blinded assessor at 12 and 24 months by comparing post randomisation assessment to baseline photographs (if patients consented), or assessed clinically if consent has not been given for photographs: 
 
- Adults: scarring worsened (yes/no).
 
- Children and adolescents: failure of normal vulval development (clinical assessment) and/or evidence of scarring (yes/no)
 
 
 

 Symptoms of LS in women and girls include (but are not limited to) itching, burning, pain, painful sexual intercourse, pain on defecation.

	
 
• Vulval Architectural Severity Scale (VASS) at 12 and 24 months post randomisation.
 
• Time to first flare.
 
• Clinician global severity assessment of LS (5-point ordinal scale) at 3, 6, 12, 18 and 24 months. Plus assessed by blinded assessor at 12 and 24 months.
 
• Condition specific Quality of Life (QoL) at 3, 6, 12, 18 and 24 months using:             
 
- Vulvar Quality Life Index (VQLI) (adults)
 
- Children’s Dermatology Life Quality Index (CDLQI) (adolescents and children).
 
 
 
• Sexual function (adults only) using Female Sexual Function Index at 12 and 24 months.
 
 
Safety
 
 
• Adverse reactions e.g. stinging, skin thinning measured by patient reported symptoms and clinical examination from randomisation over 24 months.
 
• Development of vulval intraepithelial neoplasia or vulval squamous cell carcinoma at 24 months.
 
 
Treatment acceptability and potential barriers/facilitators to treatment
 
 
• Acceptability of treatment strategy at 12 and 24 months using a Likert scale.
 
• Adherence to treatment at 3, 6, 12, 18 and 24 months.
 
• Qualitative interview sub-study at 12 months.
 
 
Cost-effectiveness
 
 
• Generic utility instrument to measure QoL at 3, 6, 12, 18 and 24 months with EQ-5D-5L (adolescents and adults) and Child Health Utility Instrument - Nine dimensions (CHU-9) (children).
 
• Resource use including prescription, direct and indirect healthcare and out-of-pocket costs associated with vulval LS at 3, 6, 12, 18 and 24 months.
 

Statistical methods
	
Primary analysis will compare the number of flares per person-time between the treatment groups, with analysis according to the allocated treatment strategy regardless of adherence to the strategy (intention-to-treat). Negative binomial regression, adjusted for minimisation factors and incorporating exposure time (person-time), will be used to calculate the incident rate ratio and 95% confidence interval. Supplementary analyses for the primary outcomes will use

	
per-protocol or complier average causal effect (CACE) analysis to estimate the effect of the intervention among the participants who complied with their allocated intervention. Exploratory subgroup analyses for the primary outcome will be performed according to age at randomisation (children or adult), time since last flare, and strength of prescribed TCS (potent or superpotent), by including appropriate interaction terms in the primary model. Between-group comparison of secondary outcomes will be based on an appropriate regression model for the outcome (or appropriate non-parametric estimator), adjusted for the same variables as the primary analysis. A full statistical analysis plan will be developed and approved by the Trial Steering Committee (TSC) prior to database lock.

Health economics
	
Primary analysis undertaking a within-trial all-age cost effectiveness analysis estimating the incremental cost per flare averted from an NHS and Personal Social Services (PSS) perspective. Secondary cost utility analyses will be undertaken for those aged 12 and over, using the EQ-5D-5L to estimate Quality Adjusted Life Years (QALYs) and separately a cost utility analysis for those aged 11 years and under using the CHU-9D to estimate QALYs. Sensitivity analyses will be undertaken to explore the impact of missing data, a wider perspective, adherence and other uncertainties detailed in the health economic analysis plan.

## ABBREVIATIONS

ACT	Anatomical Therapeutic Chemical Classification
ADR	Adverse Drug Reaction
AE	Adverse Event
CACE	Complier Average Causal Effect
CDLQI	Children’s Dermatology Life Quality Index
CEA	Cost Effectiveness Analysis
CEAC	Cost Effectiveness Acceptability Curve
CF	Informed Consent Form
CGH	Community Gynaecological Hub
CHU-9D	Child Health Utility Instrument - Nine dimensions
CI	Chief Investigator overall
e-CRF	Electronic/Case Report Form
CUA	Cost Utility Analysis
DAP	Data Analysis Plan
DMC	Data Monitoring Committee
DMP	Data Management Plan
DSUR	Development Safety Update Reports
EOT	End of Trial
EQ-5D-5L	EuroQol-5 Dimension 5 Level
FTU	Fingertip Unit
GCP	Good Clinical Practice
GP	General Practitioner
ICER	Incremental Cost Effectiveness Ratio
IMP	Investigational Medicinal Product
ISF	Investigator Site File
QALY	Quality-Adjusted Life Year
LAG	Lay Advisory Group
LS	Lichen Sclerosus
MA	Marketing Authorisation
MHRA	Medicines and Healthcare products Regulatory Agency
MICE	Multiple Imputation by Chained Equations
MP	Monitoring Plan
NCTU	Nottingham Clinical Trials Unit
NHS	National Health Service
NIHR	National Institute for Health Research
P/GIS	Parent / Guardian Information Sheet
PI	Principal Investigator at a local centre
PIC	Participant Identification Centre
PIS	Participant Information Sheet
PPI	Patient and Public Involvement
PSS	Personal Social Services

QALYs	Quality-Adjusted Life Years
QoL	Quality of Life
R&D	Research and Development department
RA	Risk Assessment
RCT	Randomised Controlled Trial
REC	Research Ethics Committee
SAE	Serious Adverse Event
SAP	Statistical Analysis Plan
SAR	Serious Adverse Reaction
SCC	Squamous Cell Carcinoma
SmPC	Summary of product Characteristics
SUSAR	Suspected Unexpected Serious Adverse Reaction
TCS	Topical Corticosteroid
TMG	Trial Management Group
TMF	Trial Master File
TSC	Trial Steering Committee
UK	United Kingdom
USM	Urgent Safety Measure
VASS	Vulvar Architectural Severity Scale
VIN	Vulval Intraepithelial Neoplasia
VQLI	Vulvar Quality Life Index

## DEFINITIONS

EMIS & SystemOne	Healthcare software, information technology and related services in the UK, electronic healthcare record system.
REF	Method used in pilot phase for data to be analysed rapidly using framework analysis (REF).
QSR NVivo	Qualitative data analysis software.
Flare	Worsening of symptoms requiring increased application of TCSs as reported by participants via two weekly reminders.
Clinical or biopsy confirmed diagnosis of vulval LS	Clinical diagnosis by an expert by findings of typical clinical features on examination, or by findings on histological examination when assessed by a histopathologist. The trial team will collect information at baseline on clinical vs histological diagnosis.
Resolution of LS symptoms	No more itching/discomfort (resolution of symptoms) as well as improvement of visual signs of flare (bruising under the skin, fissures, skin thickening) back to normal.
End of flare	Participant stops using their topical corticosteroids due to resolution of LS symptoms.
Rescue TSC use	Application once daily until symptoms and signs of active LS resolve (typically 7 days).

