### 4.3 Primary endpoint

Number of flares over 12 months. Flare is defined as worsening of symptoms requiring increased application of TCSs as reported by participants via two weekly reminders.

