## 8 TRIAL TREATMENT AND REGIMEN

Trial participants will be allocated to either 'Proactive' or 'Reactive' treatment arm. In the 'Proactive' arm, participants will be prescribed their TCS by their treating physician twice a week for 24 months, regardless of presence of LS symptoms. In the 'Reactive' arm, participants will be allocated to use their TCS only when LS symptoms (or increase in visual signs) are present (please refer to table below for more details). The choice of TCS will be at the discretion of the treating physician. Repeat prescriptions will be obtained by participants as per the usual care.

*Table 6. Intervention vs comparator group*

Treatment group	Proactive Intervention group	Reactive Comparator group
Treatment name	Superpotent or potent topical corticosteroid	Superpotent or potent topical corticosteroid
Formulation	Cream/ointment	Cream/ointment
Dosage	1 application twice-weekly on two non-consecutive days in the absence of symptoms. If symptoms flare, apply once a day until symptoms resolve.	Only use during flare. Apply once a day until symptoms resolve.
Route of administration	Topical (application of a thin layer on affected area)	Topical (application of a thin layer on affected area)
Sourcing	Provided directly as per usual care	Provided directly as per usual care
Packaging and labelling	Topical steroid will be provided and labelled as per usual care prescription, and as required for each patient	Topical steroid will be provided and labelled as per usual care prescription, and as required for each patient

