Topical dosage of TCSs for both trial groups will be recommended in Fingertip Units (FTU) depending upon area affected by LS (typically 0.5-1 FTU). FTU is the amount of topical steroid (ointment or cream) that is applied along an adult's fingertip to the first crease in the finger. One FTU is sufficient to treat an area of skin twice the size of the flat of an adult's hand with the fingers together (i.e. a 'handprint'). FTU is also used to treat an area of skin on a child. Participants in the 'Proactive' arm will use the recommended amount of their TCS twice per week on a scheduled time of the day. Participants in the 'Reactive' arm will use the recommended amount of their TCS but only when required. If participants are identified to have a flare (regardless of their group allocation) they will be instructed to use the recommended amount once a day until their symptoms subside up to one month. The treating physician will advise on the dosage for adults or children.

All participants will have received advice, as part of clinical care, on a good vulval hygiene routine including avoidance of irritants and the use of emollient as a soap substitute and barrier/moisturiser. The choice of emollient will be usual medical practice for that recruiting site. If, in the proactive arm, a participant forgets to apply their treatment, they should use their ointment/cream as soon as they remember it, provided there is a gap of at least 24 hours between the doses.

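### The only end-of-flare definition cannot be met by a proactive participant on the allocated regimen, so successive flares are not separated alike in the two arms

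*Protocol*

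**What the plan says.** - **Endpoint.** Section 4.3: "Number of flares over 12 months". The count is participant-reported, by reminders every two weeks for 12 months (Table 2; section 8.1).
- **Start of a flare.** Definitions: "Worsening of symptoms requiring increased application of TCSs as reported by participants via two weekly reminders".
- **End of a flare.** Definitions: "Participant stops using their topical corticosteroids due to resolution of LS symptoms". This is the only entry that says when a flare is over.
- **Resolution.** Definitions, as a separate entry: "No more itching/discomfort (resolution of symptoms) as well as improvement of visual signs of flare", with those signs returning to normal.
- **Proactive regimen.** Section 8 prescribes corticosteroid "twice a week for 24 months, regardless of presence of LS symptoms". Table 6 adds: "If symptoms flare, apply once a day until symptoms resolve".
- **Reactive regimen.** Table 6: "Only use during flare. Apply once a day until symptoms resolve".
- **Length of flare treatment, both arms.** The text after Table 6 has daily use continue "once a day until their symptoms subside up to one month".
- **Planning rates.** Section 10.1 assumes 4 flares per patient per year in the reactive arm and 3 in the proactive arm, with dispersion 0.34.

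**The concern.** A count of recurrent episodes needs two rules: when an episode starts, and when it is over, so that the next report of symptoms can be classed as the same episode or a new one. The start rule works in both arms, because increased application is judged against the participant's current use. The end rule does not. In the reactive arm, stopping corticosteroid and the end of the flare coincide. In the proactive arm, a participant whose flare has settled goes back to twice-weekly use and does not stop.

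Whoever answers or processes a fortnightly report in the proactive arm therefore has no stated end rule to apply. One participant may treat two bouts as one continuing flare; another may report one long bout in consecutive fortnights. Participants know their allocation and no blinded assessor sees this outcome, so nothing downstream corrects a difference between arms. The same count feeds the primary economic result, cost per flare averted (section 12). Time to first flare depends only on the first onset and is not affected.

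**Working it through.** **1. The plan's own figure.** Inputs from section 10.1: rates 4 and 3 per year, dispersion 0.34, 90% power, two-sided 0.05, 1:1 allocation. For two negative binomial rates over one year:

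n per arm = [1.960·√V0 + 1.282·√V1]² / (ln 0.75)²

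- V1 = 1/4 + 1/3 + 2×0.34 = 1.263
- V0, at the pooled rate 3.5, = 2/3.5 + 2×0.34 = 1.251
- n = 159.5, so 160 per arm and 320 in total
- 320/0.8 = 400

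Both stated figures reproduce. They presuppose a proactive mean of 3, which requires repeat flares to be counted in that arm.

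**2. The rule set against each regimen.**

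| | Reactive | Proactive |
|---|---|---|
| Use without symptoms | none | twice weekly |
| Use in a flare | once daily | once daily |
| Use after the flare settles | none | twice weekly |
| Participant stops corticosteroid? | yes | no |
| End-of-flare definition met? | yes | no |

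**3. Why the end rule is needed.** Reports come every 14 days. A flare treated for a month (about 30 days) covers 30/14 = 2.1 reporting intervals, so it touches at least three. Even a flare of 7 days, the typical length of daily use given in the Definitions, crosses a report boundary with probability 7/14 = 0.5 if its start falls at random within the interval (an assumption). Carry-over between reports would then be common.

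**4. Possible size, in both directions.** The documents give no misclassification rate, so the 10% and 25% below are assumptions. Suppose that, beyond anything shared by both arms, a fraction d of proactive flares is counted twice, or a fraction m is merged into the flare before. The rate ratio is multiplied by 1 + d or by 1 − m.

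| Excess in the proactive arm | True ratio 0.75 | True ratio 1.00 |
|---|---|---|
| 10% double-counted | 0.75×1.10 = 0.83 | 1.10 |
| 25% double-counted | 0.75×1.25 = 0.94 | 1.25 |
| 10% merged | 0.75×0.90 = 0.68 | 0.90 |
| 25% merged | 0.75×0.75 = 0.56 | 0.75 |

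**5. The literal reading, as illustration only.** Suppose that a proactive participant could contribute at most one flare. The mean count would be 1 − (1 + 0.34μ)^(−1/0.34).

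- μ = 3: 1 − 2.02^(−2.94) = 0.87; ratio to 4 is 0.22, against the planned 0.75.
- μ = 4 (no true effect): 1 − 2.36^(−2.94) = 0.92; ratio to 4 is 0.23, against 1.00.
- No true effect, with only 10% or 25% of proactive participants so limited (assumed fractions): 1 − 0.10×0.77 = 0.92 and 1 − 0.25×0.77 = 0.81.

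A mean of 0.87 cannot be squared with the 3 in section 10.1, so the literal definition contradicts the plan's own rate. The same conflict shows that the planners did not intend that reading.

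**The case against.** The strongest reply is that the definition does no work in the count. It appears only in the Definitions; section 4.3, the outcome and assessment tables, data collection and the analysis sections never refer to it. Flares are identified by onset, and a proactive participant who moves from twice-weekly to daily use again meets the onset rule again. The intended meaning can also be inferred: Table 6 ends daily use in both arms when symptoms resolve, and the definition ties stopping to resolution. Detailed counting rules may sit in the statistical analysis plan, the data management plan or the prompt text, none of which is shown.

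Much of this stands. A reader might infer that a first proactive flare never ends, that the proactive count cannot exceed one, and that a treatment effect is thereby created. The protocol does not support that: nowhere must a flare have ended before the next is counted, and section 10.1 expects repeat proactive flares. Nor is the direction known, since double-counting would work against the proactive arm. Flare onset rests on symptoms while resolution also requires signs, but this applies equally to both arms and is secondary.

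The reply does not remove the defect. The onset rule says when a flare starts, not whether symptoms in the next report belong to the same one. The protocol does state an end rule, and it fits one arm only; this is an error in stated text, not detail left to another document. Section 10.2 requires the analysis plan only before database lock, which may come after the fortnightly data are in, and an analysis plan cannot recover what the prompt did not ask.

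**Conclusion.** The point holds as an inconsistency between the Definitions and section 8 that bears on the primary outcome. A proactive participant who follows the allocation cannot satisfy the end-of-flare definition, so the stated text does not separate successive flares in the same way in the two arms. The outcome is an open-label, participant-reported count and the planned effect is a ratio of 0.75, so even modest arm-specific merging or double-counting would matter.

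The size and direction of any bias are not determined by the documents. The figures in step 4 rest on assumed error fractions. The ratios in step 5 rest on a literal reading that section 10.1 contradicts and do not predict the trial's result. The conclusion assumes that participants follow the regimen and that the unseen prompt does not already use an end rule common to both arms; if it does, the remaining fault is the protocol wording.

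**What to change.** Reconcile the end-of-flare and resolution entries in the Definitions with Table 6 and the text that follows it in section 8. Then, for outcome counting only:

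1. Define the end of a flare in terms that work in both arms: symptoms resolved and corticosteroid use back to the allocated regimen. In the reactive arm that means no use, so the present meaning is kept there; in the proactive arm it means the twice-weekly schedule.
2. Count a new flare only after the previous one has ended by that rule, and say so in section 4.3.
3. Check the fortnightly prompt and use the same wording in both arms, so that each report shows whether a flare is new or continuing.
4. State whether the counting rule requires signs as well as symptoms to have resolved, alike in both arms.

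This changes no treatment instruction. It costs a wording amendment and a check of the prompt, with no extra visits or participants, and 320/400 stands. If fortnightly data have already been collected, document how earlier reports were classed, without reference to allocation where possible.
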